7.5.5 Response under secondary efficacy criteria

Overall response rates during the whole study will be provided for each treatment group and all.

7.6 Safety

Analysis of safety will be based on All Treated Subjects and presented by treatment (“as treated”) and overall.

Adverse events (AEs) will be coded according to the most current version of MedDRA and be graded using the NCI Common Terminology Criteria for Adverse Events (CTCAE) version 4.0. Drug-related AEs are those events with relationship to study drug “Related” as recorded on the CRF. If the relationship to study drug is missing, the AE will be considered as drug-related.

Listing of adverse events will include all enrolled subjects as SAEs and deaths are collected pretreatment. Summaries of adverse events will include (1) events occurring from the first dose date to 35 days (inclusive) after the last dose of BMS-986004 for subjects who are off study

treatment and (2) all events occurring from first dose date for subjects who are still on study medication.

When reporting adverse events by CTC grade, summary tables will be provided based on the event with worst CTC grade (independent of relationship to study medication). Subjects will only be counted (1) once at the preferred term (PT) level, (2) once at the system organ class (SOC) level, and (3) once in the 'Total subject' row at their worst CTC grade, regardless of SOC or PT.

The analysis of laboratory results will be based on All Treated Subjects. Laboratory results will be categorized according to NCI CTCAE (version 4.0) grade. Baseline is defined as the last non-missing measurement prior to the first dosing date and time. Summaries of laboratory results include baseline and (1) post-baseline results up to 35 days (inclusive) after the last dose of BMS-986004 for subjects who are off study treatment and (2) all available post-baseline results for subjects who are still on study medication.

7.6.1 Overall Adverse Events

AEs will be tabulated by descending frequency of SOC and descending frequency of PT within each SOC, unless specified otherwise.

Summary:

Overall summary of any AEs by worst CTC grade (grade 1, 2, 3, 4, 5, unknown) presented by SOC/PT for each treatment group and arm.

Listing:

All recorded Adverse Events occurring in the pre-treatment, on-treatment, and post treatment period will be listed.

7.6.2 Deaths

Summary:

All deaths during the study within 35 days after the last dose of BMS-986004 will be summarized for cause of deaths by treatment group and arm.

Listing:

All recorded deaths during the study, including post-treatment follow-up period, and deaths that resulted from a process that began during the study, will be listed.

7.6.3 Serious Adverse Events

Summary:

Overall summary of SAEs by worst CTC grade (grade 1, 2, 3, 4, 5, unknown) presented by SOC/PT for each treatment group and arm.

Listing:

By-subject SAE listing will be provided for the All Enrolled Subjects.

7.6.4 Adverse Events Leading to Discontinuation of Study Therapy

Adverse events leading to study drug discontinuation are AEs with action taken = “Drug was discontinued”.

Summary:

Overall summary of AEs leading to discontinuation by worst CTC grade (grade 1, 2, 3, 4, 5, unknown) presented by SOC/PT

Listing:

By-subject AEs leading to discontinuation listing will be provided.

7.6.5 Multiple Events

Analyses that take into account the multiple occurrences of a given adverse event will be conducted. In order to prepare these analyses, the CRF data will be processed according to standard BMS algorithms in order to collapse adverse event records into unique records based on the preferred term. This data will be presented as the rate per 100 patient-years of exposure. This analysis will take into account all on-treatment events (allowing more than 1 event per subject) and the total duration of exposure. The patient-years exposure will be computed as the sum over the subjects’ exposure expressed in years where the duration of exposure is defined as

- Date of last dose of study treatment - date of first dose of study treatment +35 + 1 days, for subject who are off study treatment and were followed at least 35 days after last dose of study medication.
- Last known date alive - date of first dose of study medication +1, for subjects who are still on-treatment or who are off study treatment and were followed less than 35 days after last dose of study medication.

Summary:

The following summary tables will be provided for each arm:

Total number and rate (exposure adjusted) of occurrences for all AEs occurring in at least 5% of the subjects treated in the arm.

For select AEs, if applicable:

Tables showing the number of subjects experiencing an AE once or multiple times in each arm

Listing:

Unique instances of all AEs, i.e., after duplicates have been eliminated and overlapping and contiguous occurrences of the same event (i.e. same PT) have been collapsed.

7.6.6 Select Adverse Events

Select AEs under different categories, if present, will be summarized by the following table for each treatment group and arm:

- Overall summary of any select AEs by worst CTC grade presented by category/PT (any grade, grade 3-4, grade 5)

The list of all select AE and the grouping category, if available, will be provided in a separate document, data presentation plan.

7.6.7 Clinical Laboratory Evaluations

Clinical laboratory data will be first analyzed using International System of Units (SI). Analyses will be repeated using US conventional units.

Summary:

The number (%) of subjects with the following will be summarized by treatment group and arm, if appropriate, using the worst CTC grade on-treatment per subject for each gradable lab test.

- Post-baseline grade
- Grade change from baseline
- Descriptive statistics of laboratory test result and their changes from baseline by treatment and study day

Listing:

A by-subject listing of these laboratory parameters will be provided

7.6.8 Thromboembolism (TE) Safety Biomarker

Thromboembolism safety biomarkers include Prothrombin time (PT), activated Partial thromboplastin time (aPTT), D-dimer, thrombin antithrombin (TAT), and Serum troponin I. Among the above safety biomarkers, PT and aPTT are collected during screening, and others are collected longitudinally on select study days.

TE safety biomarkers will be listed for all treated subjects in ascending order of collection day.

7.6.9 ECG

All of the available ECG parameter values from each subject will be provided in a listing. Abnormal findings of ECG will be presented separately.

7.6.10 Vital Signs

Vital signs parameters (systolic blood pressure, diastolic blood pressure, heart rate, respiratory rate and body temperature) will be listed for all treated subjects.

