1.5.4 Risk of Infusion Reactions

As with any biological product, infusion reactions are a risk, even following a single dose. To reduce the risk of infusion reactions, patients will be closely monitored by trained personnel experienced with treatment of anaphylaxis and lesser infusion reactions. In addition, IV administration of study drug will not exceed infusion rate of 12.5 mg/min (Table 4-1). Furthermore, patients with history of any significant drug allergy or serious adverse reaction or hypersensitivity to any IV administered biologic will be excluded from the study.

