4 STUDY DRUG

Study drug includes Investigational [Medicinal] Product (IP/IMP) and Non-investigational [Medicinal] Product (Non-IP/Non-IMP) and can consist of the following:

- All products, active or placebo, being tested or used as a comparator in a clinical trial.
- Study required premedication, and
- Other drugs administered as part of the study that are critical to claims of efficacy (eg, background therapy, rescue medications)
- Diagnostic agents: (such as glucose for glucose challenge) given as part of the protocol requirements must also be included in the dosing data collection.

BMS-986004 will be administered as a solution intravenously. Table 4-1 below indicates the total dose and number of vials per dose for each.

Table 4-1: Treatment Administration

Treatment	Total Daily Dose	Volume of Reconstituted 50 mg/mL BMS-986004	Number of BMS-986004 Vials	Prime Filter	Infusion Volume (mL)	Infusion Time (min)	Rate (mg/min)
1	75 mg IV	3 mL	1	YES	50	120	0.625
2	225 mg IV	4.5 mL	2	NO	100	120	1.875
3	675 mg IV	13.5 mL	4	NO	100	120	5.625
4	1500 mg IV	30 mL	8	NO	100	120	12.500

Table 4-2: Treatment Administration During Long Term Extension

Total Daily Dose	Volume of Reconstituted 50 mg/mL BMS-986004	Number of BMS-986004 Vials	Prime Filter	Infusion Volume (mL)	Infusion Time (min)	Rate (mg/min)
1500 mg IV	30 mL	8	NO	100	120	12.500

The study drug should be dispensed by the pharmacist or qualified designee and administered as an infusion using an infusion pump. Do not ever administer study drug by intravenous push (IVP) or bolus injection. A physician must be present at the infusion site during all administrations of study drug.

Vital signs (blood pressure, heart rate, respiratory rate, and temperature) will be monitored before infusion (at anytime the day of dosing, prior to infusion), approximately every 15 minutes during infusion, at the end of the infusion (within 10 minutes after the infusion has stopped), and approximately every 30 minutes after completion of the infusion until stable, as judged by the investigator. If an anaphylactoid-like infusion reaction or anaphylactic reaction occurs, vital signs will be taken more frequently, as warranted by the severity of the reaction. Blood pressure and heart rate will also be taken prior to discharge from the site on visits in which study drug is administered.

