8.3 Endpoints

8.3.1 Primary Endpoint(s)

The primary objective to establish safety will be measured by the primary endpoints of AEs, SAEs, ECG, and laboratory abnormalities including safety biomarkers of d-Dimer and TAT. These endpoints will be based on medical reviews of AE reports and the results of vital sign measurements, physical examinations, clinical laboratory tests, and ECG parameters including heart rate, PR interval, QRS interval, and QTcF interval (QT interval corrected for heart rate).

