8.4.3 Safety Analyses

All recorded adverse events will be listed and tabulated by system organ class, preferred term and treatment. Vital signs and clinical laboratory test results will be listed and summarized by treatment. Any significant physical examination findings, and clinical laboratory results will be listed. ECG readings will be evaluated by the investigator and abnormalities, if present, will be listed.

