4.2 Safety Endpoints

Safety endpoints include incidence of AE at the highest grade, death as well as marked abnormalities in clinical laboratory tests, vital sign measurements, ECGs, and physical examinations. Incidence of AEs is provided separately for overall AEs, serious AEs, and AEs leading to discontinuation.

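### The SAP plans only a listing of vital signs, although the protocol promises a summary by treatment and the SAP makes their marked abnormalities a safety endpoint

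*SAP*

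**What the plan says.** Protocol 8.4.3 (Safety Analyses) states: "Vital signs and clinical laboratory test results will be listed and summarized by treatment". The synopsis makes the same commitment. Protocol 8.3.1 bases its safety endpoints on medical review of adverse event reports together with "the results of vital sign measurements, physical examinations, clinical laboratory tests, and ECG parameters".

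SAP 4.2 defines the safety endpoints as the incidence of adverse events and "death as well as marked abnormalities in clinical laboratory tests, vital sign measurements, ECGs, and physical examinations".

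SAP 7.6.10, the only section on vital signs, covers systolic and diastolic blood pressure, "heart rate, respiratory rate and body temperature) will be listed for all treated subjects". It plans nothing else.

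SAP 7.2 says that changes from the analysis specified in the protocol will be defined in the SAP. None is stated for vital signs.

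**The concern.** Safety is the primary objective, and the design compares four ascending dose panels. The protocol says vital signs will be summarised by treatment, so a reader expects to see values and changes side by side by dose. The SAP drops that summary without comment and leaves one of its own named endpoints with no definition and no count.

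A by-subject listing lets a reviewer find an extreme value in one subject. It does not show a shift in mean blood pressure or heart rate from baseline in one dose group, or how many subjects per group crossed a limit. If such a change is too small or too brief for an investigator to report as an adverse event, no planned output would bring it out.

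**Working it through.** No sample size, error rate or model is involved, so the check compares texts.

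**Step 1. What the protocol promises and what the SAP delivers, by type of data**

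| Data | Protocol 8.4.3 | SAP |
|---|---|---|
| Laboratory tests | Listing and summary by treatment | 7.6.7: listing, worst grade and grade change per group, descriptive statistics and change from baseline by treatment and day |
| Vital signs | Listing and summary by treatment (same sentence as laboratory tests) | 7.6.10: listing only |
| ECG | Abnormalities listed | 7.6.9: listing, abnormal findings shown separately |
| Physical examination | Significant findings listed | 7.6.11: abnormal findings listed |

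Of these four, only vital signs fall short of the protocol. One protocol sentence covers laboratory tests and vital signs together, and the SAP carries over the summary for laboratory tests alone.

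**Step 2. Is the endpoint derived anywhere?** SAP 4.2 names "marked abnormalities in clinical laboratory tests, vital sign measurements, ECGs, and physical examinations". For vital signs, the visible SAP text gives no limit defining a marked abnormality, no count of subjects, and no summary of values or of change from baseline.

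**Step 3. Does another section supply the summary?**
- SAP 7.1 gives the statistics used for continuous variables in general. It commits to no vital-sign table.
- The opening of SAP 7.6 says safety will be presented by treatment and overall. That sets the grouping of whatever is produced, and for vital signs 7.6.10 produces only a listing.
- Where the authors wanted a summary as well as a listing, they said so, as in SAP 7.3.3 (physical measurements) and 7.6.7 (laboratory tests).

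**Step 4. What is summarised through adverse events?** SAP 7.6.1 and 7.6.3 tabulate adverse events and serious adverse events by worst grade, organ class and preferred term for each treatment group. SAP 7.6.4 does the same for events leading to discontinuation, and SAP 6.2 applies treatment grouping to all non-PK summaries. An infusion effect reported as an adverse event is therefore counted by group. What remains is measured change not recorded as an event.

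**Step 5. Amount of scheduled data.** Protocol Table 5.1-2 marks vital signs at 14 visits: Days 1, 2, 4, 8, 15, 29, 43, 57, 71 and 85, and four follow-up visits. SAP 7.6.10 names 5 parameters, and 40 subjects are planned.

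14 × 5 × 40 = 2,800 values if every subject attends every visit. Subjects who enter the extension skip the four follow-up visits and contribute 10 × 5 = 50 values each instead of 14 × 5 = 70, so 2,800 is an upper figure for 40 subjects. It describes how much data is only listed. It does not measure bias.

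**The case against.** The strongest reply is that the adverse event tables do the work. Protocol 6.7 asks that significant worsening on any safety assessment, whether or not the protocol requires it, be recorded as an adverse event. A serious vital-sign change should therefore reach tables presented by treatment group. This stands, and it limits the gap to changes not judged or recorded as events. It does not close the gap, because SAP 4.2 lists marked vital-sign abnormalities separately from adverse events.

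Table details are left to a data presentation plan that is not among the documents, and it may contain a vital-sign table. However, SAP section 8 bases the report's statistical content on the SAP, which does not require one.

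The SAP reflects the protocol through Amendment 02. The protocol at hand has a long-term extension and an 8-week follow-up, against 4 weeks in the SAP, so it appears to be later. Whether the sentence in 8.4.3 stood in the version the SAP implements cannot be checked. The mismatch within the SAP, between 4.2 and 7.6.10, does not depend on this.

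A reader might infer more than the documents support:

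- *That infusion effects get no planned summary at all.* Those reported as adverse events do.
- *That vital signs are a named primary endpoint.* Protocol 8.3.1 names adverse events, serious adverse events, ECG and laboratory abnormalities. Vital signs appear in the next sentence, as material for medical review.
- *That an infusion effect ought to appear as a dose trend.* Protocol Table 4-1 gives every panel 120 minutes, so the rate rises from 0.625 to 12.5 mg/min (12.5 / 0.625 = 20-fold), and 1.5.4 says: "As with any biological product, infusion reactions are a risk, even following a single dose". But the documents do not say that reactions depend on rate or dose. Protocol 1.5.1 places them under immunogenic potential, section 4 allows premedication after a reaction, and each panel has 10 subjects with no control.
- *That a large body of within-infusion data goes unused.* Protocol section 4 has vital signs monitored "approximately every 15 minutes during infusion, at the end of the infusion", but neither document shows that these readings enter the database.

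**Conclusion.** The concern holds in a limited form. As written, the SAP omits a summary by treatment that the protocol promises, leaves the vital-sign endpoint in SAP 4.2 without a definition or a count, and does not declare the change. Dose-related changes in vital signs that are not recorded as adverse events therefore have no planned summary.

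The effect on the trial's conclusions cannot be put in numbers from the documents. At most about 2,800 scheduled short-term values are affected, assuming 40 subjects attend all 14 visits. The conclusion rests on the visible SAP text and on the data presentation plan not being a binding substitute for it. The correction is worth making because safety is the primary objective and the scheduled-visit data are already collected.

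**What to change.** In SAP 7.6.10, keep the listing and add:

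1. Descriptive statistics of each vital sign and its change from baseline, by treatment group and scheduled study day, in the form SAP 7.6.7 uses for laboratory tests.
2. The number of subjects per treatment group with a marked abnormality, using limits chosen by the sponsor and fixed before database lock, so that the endpoint in SAP 4.2 is computed.

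Grouping by planned starting dose follows SAP 6.2. Because some subjects move to a higher dose from Day 57, the tables should state which dose defines the group.

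If readings during infusion are captured in the database, a summary of change from the pre-infusion value by the dose infused may be added. This is optional and goes beyond what the protocol promises.

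If the sponsor prefers a listing alone, it should declare and justify the departure under SAP 7.2 and reconcile SAP 4.2 with it.

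The cost is a paragraph of SAP text, agreement on the limits, and two tables. No new data are needed for the two required tables, and no dose or clinical procedure changes.

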7.6.11 Physical Examination Findings

All physical examination abnormal findings will be listed per subject and visit.

7.7 Pharmacokinetics

PK sampling date and time are shown below in [Table 7.7-1](#) for convenience. On day 57, non-responders in each treatment group other than the 1500mg group will be dose-escalated to the starting dose of the next higher treatment group.

The Pharmacokinetic (PK) population will be used for all listings. Evaluable PK population will be used for summaries. PK parameters and C_{trough} will be summarized for each group decided by current dose, and dose proportionality analysis will be provided by excluding subjects who have dose escalation on day 57.

Table 7.7-1: PK Sample Study Day and Time

study day	dosing	PK Sampling
1	#1, at starting dose	0h, 2h, 24h, 72h, 168h
15	#2, at starting dose	0h
29	#3, at starting dose	0h
43	#4, at starting dose	0h, 168h
57	#5, Responder: at starting dose Non-Responder: at titration dose	0h, 2h
71	#6, at the same dose as Day 57	0h, 2h, 24h, 96h, 168h
85	#7, at the same dose as Day 57	0h, 336h, 672h

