3.1.1 Intra-subject dose escalation

Intra-subject dose escalation could occur after the subject has completed the Response Phase of the study. The intra-subject dose escalation decision will be based on review of the safety information and platelet count after 4 weeks of treatment. The decision to escalate dose for the subject will be made after evaluating platelet count at Day 50, 7 days after the 4th dose of BMS-986004 has been administered. Subject will receive the next higher dose of BMS-986004 if clinically significant response has not been achieved based on measurement of platelet count on

the last two consecutive counts performed at Day 43 and Day 50, and a favorable safety profile is observed (see Table 3.1.1-1). Clinically significant response is defined as achieving platelet count $\geq 50,000/\text{mm}^3$ with an increase of at least $20,000/\text{mm}^3$ from baseline and absence of bleeding. Subject will then be dosed at the higher dose level for the remainder of the study (Remission Phase), receiving investigational product at that dose on Week 8, Week 10 and Week 12. Active treatment period with BMS-986004, regardless of the dose, may not exceed 12 weeks for any individual subject.

Table 3.1.1-1: Dose Adjustment after Response Phase

Platelet Count at Day 43 and Day 50 (7 days after the 4th dose) (X /mm³)	Action
< 50,000	Dose increase, as indicated by the next dose panel
$\geq 50,000$ with an increase of at least 20,000 from baseline	Dose remains constant on bi-weekly schedule

3.1.2 Dose frequency adjustment for responders exceeding 450,000/mm³ (for non-splenectomized subjects) and 600,000/mm³ (for splenectomized subjects) platelet count

For both the Short Term Study and the Long Term Extension plan, in the event that platelet count exceeds $450,000/\text{mm}^3$ for non-splenectomized subjects and $600,000/\text{mm}^3$ for subjects who underwent splenectomy, in the absence of recent (administered within two weeks) rescue medication, as indicated by the two consecutive platelet count measurements, dosing of the BMS-986004 should be stopped. Subject will remain in the study and platelet counts will be then assessed based on the normal study visit schedule. Dosing of BMS-986004 could be reinitiated only after discussion between Study Director and Investigator if clinically appropriate and dictated by the medical judgment and subject’s safety.

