5.5.1 Pharmacokinetics: Collection and Processing

Table 5.5.1-1 lists the sampling schedule to be followed for the assessment of pharmacokinetics. Further details of blood collection and processing will be provided to the site in the procedure manual.

Table 5.5.1-1: Pharmacokinetic Sampling Schedule for BMS-986004

Study Day/Month of Sample Collection	Event	Time (Relative To BMS-986004 Dose) Hour: Min	BMS-986004 Blood Sample	BMS-986004 Immunogenicity Sample
Collections During Short-Term Period				
1	Predose	00:00	X	X
1	EOI ^a	02:00	X	
2		24:00	X	
4		72:00	X	
8		168:00	X	
15	Predose	00:00	X	X
29	Predose	00:00	X	X
43	Predose	00:00	X	X
50		168:00	X	
57	Predose	00:00	X	X
57	EOI ^a	02:00	X	
71	Predose	00:00	X	X
71	EOI ^a	02:00	X	
72		24:00	X	
75		96:00	X	
78		168:00	X	
85	Predose	00:00	X	X
FU 1 (Day 99)		336:00	X	X
FU 2 (Day 113)		672:00	X	X
FU 3 (Day 127)		1008:00	X	X
FU 4 (Day 141)		1344:00	X	X

Table 5.5.1-1: Pharmacokinetic Sampling Schedule for BMS-986004

Study Day/Month of Sample Collection	Event	Time (Relative To BMS-986004 Dose) Hour: Min	BMS-986004 Blood Sample	BMS-986004 Immunogenicity Sample
Collections During Long Term Extension				
LTE Day 15	Predose	00:00	X	X
LTE Day 29	Predose	00:00	X	X
LTE Day 43	Predose	00:00	X	X
LTE Day 57	Predose	00:00	X	X
LTE Day 71	Predose	00:00	X	X
LTE Day 85	Predose	00:00	X	X
LTE Day 99	Predose	00:00	X	X
LTE Day 113	Predose	00:00	X	X
LTE Day 127	Predose	00:00	X	X
LTE Day 141	Predose	00:00	X	X
LTE Day 155	Predose	00:00	X	X
LTE Day 169	Predose	00:00	X	X
Taper V1 LTE 190	Predose	00:00	X	X
Taper V2 LTE 218	Predose	00:00	X	X
LTE FU D248			X	X
LTE FU D278			X	X
LTE FU D308			X	X
Other Samples				
AE ^b	AE		X	X

^a EOI=End of Infusion, This sample should be taken immediately prior to stopping the infusion (preferably within 2 minutes prior to the end of infusion). If the end of infusion is delayed to beyond the nominal infusion duration, the collection of this sample should also be delayed accordingly. The PK serum sample of EOI must be taken on the contralateral arm.

^b For subjects who are prematurely discontinued due to AEs, the listed samples should be taken

It is expected that every effort be made to collect PK samples at the times indicated in the protocol. The following windows serve as a guideline for PK and Biomarker sample collections:

- +/- 2 minutes for samples within the first 2 hours after dose
- +/- 1 day for the 24 hour post dose time point (Day 2, Day 72)

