6.2 Treatment Groups

Treatment groups will be decided by the planned starting dose regardless of intra-subject dose escalation planned at day 57. Table 6.2-1 below indicates the planned treatment groups.

All summaries, except PK summary, will be provided by treatment group. For PK summary, it is current dose that is used to decide the dose group.

Table 6.2-1: Treatment Group

Cohort	Treatment Group Label
A	BMS 75mg
B	BMS 225mg
C	BMS 675mg
D	BMS 1500mg

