7.7.1 PK Parameters

All individual PK parameters will be listed for BMS-986004 including any exclusions and reasons for exclusion from summaries. Summary statistics will be tabulated for each PK parameters by treatment and by study day. Geometric means and coefficients of variation will be presented for C_{max}, AUC(TAU), CLT, AI_AUC, and AI_C_{max}. Decimal place specifications for summary statistics are described in [Section 7.11](#).

PK parameters will be summarized for day 1 and day 71 with the grouping decided by current dose - the planned dose on each of the two study days, as subjects are expected to have achieved steady state by day 71. Under this assumption, the PK parameters are considered to be related to the current dose, regardless of the previous doses. As such, 75mg dose group on day 71 consists of subjects dosed at 75mg only; 225mg dose group on day 71 consists of subjects from both non-responders of 75mg cohort and responders of 225mg cohort, all of whom will be dosed at 225mg; 675mg dose group on day 71 consists of subjects from both non-responders of 225mg cohort and responders of 675mg cohort; 1500mg dose group on day 71 consists all of the subjects from 1500mg cohort and also the non-responders from 675mg.

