7.7.2 Ctrough Summary

Ctrough will be listed for all available data and summarized on day 15, 29, 43, 57, 71, and 85 for each group decided by previous dose.

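### SAP 7.7 groups Ctrough by current dose and SAP 7.7.2 by previous dose; the two rules give different Day 57 trough summaries for escalated subjects, and no precedence is stated

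*SAP*

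**What the plan says.** Three places in the SAP set the dose group for PK summaries.

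- SAP 6.2 (Treatment Groups) gives the general rule: "For PK summary, it is current dose that is used to decide the dose group". It neither names Ctrough nor makes an exception for it.
- SAP 7.7 (Pharmacokinetics) names Ctrough alongside the PK parameters and says that they "will be summarized for each group decided by current dose, and dose proportionality analysis will be provided".
- SAP 7.7.2 (Ctrough Summary) says that Ctrough is "summarized on day 15, 29, 43, 57, 71, and 85 for each group decided by previous dose".

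SAP 7.7.1 explains the term for the PK parameters: "the grouping decided by current dose - the planned dose on each of the two study days", those two days being Day 1 and Day 71. It justifies the choice by expecting steady state by Day 71.

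On escalation, SAP 7.7 states: "On day 57, non-responders in each treatment group other than the 1500mg group will be dose-escalated to the starting dose of the next higher treatment", meaning the next cohort up. Protocol 3.1.1 agrees on the timing, with escalated subjects "receiving investigational product at that dose on Week 8, Week 10 and Week 12". The Day 57 row of SAP Table 7.7-1 reads "5, Responder: at starting dose Non-Responder: at titration dose". Protocol Table 5.5.1-1 lists the trough sample on that day as "57 Predose 00:00".

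**The concern.** A trough reflects the infusion before it, not the one about to be given. On Day 57 these differ for every escalated subject: the last infusion was the starting dose on Day 43, and the dose planned for that day is the titration dose. Read literally, SAP 7.7 and 6.2 would place that trough under a dose the subject has not received, while SAP 7.7.2 would place it under the dose that produced it.

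Ctrough is a secondary PK endpoint (Protocol 8.3.2). Two programmers working from the same SAP could produce different Day 57 tables, and a check against the SAP could support either. Under the current-dose rule, Day 57 troughs at 225, 675 and 1500 mg would be mixed with samples from the next lower dose, so the table could show an apparent fall from Day 43 to Day 57 that comes only from the labelling.

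**Working it through.** The plan states no figure on this point, so there is nothing to reproduce. The check has two steps.

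**Step 1: where the two rules differ.** Take a cohort A subject escalated from 75 to 225 mg on Day 57. Current dose is the dose planned for that day; previous dose is the one given at the infusion before the predose sample.

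| Trough day | Current dose (mg) | Previous dose (mg) | Same group? |
|---|---|---|---|
| 15 | 75 | 75 | yes |
| 29 | 75 | 75 | yes |
| 43 | 75 | 75 | yes |
| 57 | 225 | 75 | **no** |
| 71 | 225 | 225 | yes |
| 85 | 225 | 225 | yes |

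The rules differ on Day 57 only, and there for every escalated subject. Subjects who are not escalated fall in the same group under either rule on all six days.

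**Step 2: illustrative size on Day 57.** Inputs:

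- 10 subjects per cohort at 75, 225, 675 and 1500 mg (SAP 2.1).
- Response rates of 0.2, 0.4 and 0.55 at the three lower doses (Protocol Appendix 2), and separately the 20% to 50% range for those doses in SAP 7.7.3.
- Assumption: the share not escalated equals the response rate.
- Assumption: trough is proportional to dose.

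For dose D(i) with response rate r(i), the current-dose group holds 10 × r(i) subjects who stay (all 10 at 1500 mg) plus 10 × (1 − r(i−1)) who move in from the dose below. If f is the moved-in fraction, the ratio of the group's geometric mean to its unmixed value is (D(i−1)/D(i))^f.

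At rates 0.2, 0.4 and 0.55:

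| Group (mg) | Stay | Moved in | Total | f | Geometric-mean ratio |
|---|---|---|---|---|---|
| 75 | 2 | 0 | 2 | 0 | 1 |
| 225 | 4 | 8 | 12 | 0.667 | (75/225)^0.667 = 0.48 |
| 675 | 5.5 | 6 | 11.5 | 0.522 | (225/675)^0.522 = 0.56 |
| 1500 | 10 | 4.5 | 14.5 | 0.310 | (675/1500)^0.310 = 0.78 |

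Misplaced troughs: 8 + 6 + 4.5 = 18.5 of 40 (an expected count, hence the half).

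With one common rate in the three lower cohorts:

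| Response rate | Misplaced | Ratio at 225 mg | Ratio at 675 mg | Ratio at 1500 mg |
|---|---|---|---|---|
| 20% | 8 + 8 + 8 = 24 of 40 | (1/3)^(8/10) = 0.42 | 0.42 | 0.45^(8/18) = 0.70 |
| 50% | 5 + 5 + 5 = 15 of 40 | (1/3)^(5/10) = 0.58 | 0.58 | 0.45^(5/15) = 0.77 |

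The 0.78 at 1500 mg in the first table lies just outside the last column because the assumed 0.55 at 675 mg exceeds the SAP's upper limit of 50%.

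Under the previous-dose rule of SAP 7.7.2, the Day 57 groups are 10, 10, 10 and 10, with none misplaced.

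**The case against.** The strongest reply is that the SAP already holds a suitable rule in the section devoted to Ctrough. SAP 7.7.2 lists Day 57 and says previous dose. The sentence in 7.7 is a lead-in covering several analyses, 6.2 does not name Ctrough, and current dose is defined only for Days 1 and 71. A careful programmer may well follow 7.7.2. This stands as far as it goes: a reader might infer that the plan will mis-tabulate Day 57, and the documents do not establish that. They contain two incompatible instructions. But 7.7 names Ctrough expressly, 6.2 points the same way, and nothing says that 7.7.2 prevails.

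A reader might also infer that the dose-proportionality result would be biased. It would not: SAP 7.7.3 limits the power model to Cmax and AUC(TAU) on Days 1 and 71 and removes escalated subjects on Day 71. Nor is damage to exposure-response modelling shown. Protocol 8.4.11.2 puts that in a population analysis reported separately, and no visible text says it uses group trough summaries. No visible section bases a steady-state assessment on Ctrough either.

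The size estimate is also open to challenge, fairly. Escalation depends on a different platelet criterion (at least 50,000/mm³ with a rise of at least 20,000/mm³ and no bleeding, on Days 43 and 50) and on a favourable safety profile, so the share escalated need not equal one minus the response rate. Dose-proportional troughs are an assumption too. Protocol 3.3.1 takes five half-lives as 20 days, which is 4 days each, so a 14-day trough lies 14/4 = 3.5 half-lives after the infusion. SAP 7.11.2 sets troughs below the quantification limit to half that limit, so if low-dose troughs are often censored the ratios would differ from those above.

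Finally, Ctrough is also listed for all available data, so the table could be regrouped later.

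**Conclusion.** The contradiction is real and is in the current SAP text: 7.7, with 6.2 by its general wording, against 7.7.2. It affects one of six trough days, in a descriptive summary of a secondary PK endpoint, and only through escalated subjects. Only the previous-dose rule matches the predose sampling on that day.

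The count of 15 to 24 misplaced troughs out of 40 (18.5 at the protocol's assumed rates) depends on equating the share not escalated with the response rate. The geometric-mean ratios, from about 0.42 to 0.78 according to dose and response rate, depend also on dose-proportional troughs. They show that the choice of rule could matter by about twofold at 225 and 675 mg; they do not predict the trial's data.

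The check takes Day 57 as the first day at the escalated dose, as in the SAP and Protocol 3.1.1. The early-decision text in Protocol 3.1.4 and Appendix 1 puts the first titration dose on Day 43; those passages need to be reconciled separately.

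**What to change.** Make 7.7.2 the single rule for Ctrough.

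- In SAP 7.7, delete *and Ctrough* from the sentence that groups by current dose.
- In SAP 6.2 and 7.7, add: *except Ctrough, which is grouped by previous dose (the dose of the infusion immediately preceding the sample; see 7.7.2)*.
- Keep current dose for Cmax, AUC(TAU) and CLT.

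The cost is a short wording change in two sections, best made before the PK tables are programmed. It needs no new data and changes neither the design nor the conduct of the trial.
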